For subjects who do not convert, the last visit will occur no later than at the Month 8 visit. For subjects who do convert, the last visit will be at the visit corresponding to 12 months following their conversion dates. All subjects who discontinue study drug early should have all procedures listed in the end of treatment (EOT) visit performed, with the exception of the chest CT scan. A chest CT scan should only be performed if the subject is participating in the CT scan sub-study but only if 6 months or more have elapsed since the subject's last CT scan has been performed. Please refer to [APPENDIX 5](#) for Japan specific CT Scan Sub-Study study procedures and study schedule. High resolution CT scan is preferred, if available.

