### **9.6.3 Exploratory Endpoint Analyses**

The change in 6MWT distance at Month 6 for converters compared with non-converters overall for ITT population, within LAI plus a multi-drug regimen, within the multi-drug regimen alone, the change in BMI at Month 6 for LAI plus a multi-drug regimen compared with a multi-drug regimen alone, and the changes in chest CT scan at EOT for LAI plus a multi-drug regimen compared with a multi-drug regimen alone in a sub-set of subjects will be analyzed using the ANCOVA models with the comparison arm (converters vs. non-converters or the treatment arm) and the randomization strata as factors, and the corresponding Baseline measure as a covariate. If a CT scan is not performed at EOT for any subject, then prior CT scan will be used in the analysis.

The change from Baseline (Day 1) to Month 6 and EOT in the EQ-5D-3L patient reported health outcomes will be analyzed for the ITT population similarly using the same MMRM method as the analysis of the change from Baseline to EOT in 6MWT distance. Kaplan-Meier estimates for the distribution of time to death will be constructed by treatment arm. The treatment comparison will be made using the stratified log rank test for the ITT population. Incidence of new MAC strains will be summarized by treatment arms.

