## **Sub-Study Design**

Eligible subjects must be enrolled into the INS-212 study. At randomization (Day 1), any subject who has signed the informed consent for this chest CT Scan Sub-Study will participate; there is no maximum number of subjects that can participate. At the latest, the informed consent and the subject's Baseline chest CT scan must be collected no later than 2 weeks after the subject's first dose of LAI or multi-drug regimen in the INS-212 study. A prior chest CT scan may be used as a subject's Baseline measure if this CT scan was obtained within 6 months from the subjects Day 1 study visit. All subjects in this chest CT Scan Sub-Study will have their follow-up chest CT scan on the (EOT) visit ( $\pm 14$  days) provided the last chest CT scan was not obtained within the prior 6 months. High resolution CT scan is preferred, if available.

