### **Sub-Study Procedures**

On Day 1 ( $\pm 14$  days) subjects will be asked to provide informed consent for this sub-study. Once the informed consent has been signed the subject should have a chest CT scan performed (a prior CT scan that was obtained within 6 months prior to signing the informed consent may be used for Baseline). A CT scan should not be performed during Screening for this CT-Scan Sub-Study. It will be performed at Baseline (Day 1) once the subject is randomized. A second chest CT scan will be performed when a subject has completed treatment (EOT  $\pm 14$  days), which includes any subject that prematurely discontinues study drug provided that more than 6 months have elapsed since their last CT scan. High resolution CT scan is preferred, if available.

All chest CT scans will be read locally and a description of findings for each scan will be entered into the eCRF page. An overall assessment of improved, worsening, or no change from previous scan will be reported for all scans after the subject's Baseline scan. All chest CT scans must be made available to the Sponsor to be stored as study source documentation.

Protocol Amendment #3 version: 22 February 2016

*This protocol is solely for the purpose of communicating information about the investigational drug between Insmmed Incorporated and study personnel. Information is not to be reproduced, abstracted or used for sharing of information for any other purpose, whatsoever, except with the written permission of Insmmed Incorporated.*

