**Table 14-3 Schedule of Events for INS-212 CT Scan Sub-Study**

INS-212 CT Scan Sub-Study		
	Baseline	EOT
	(V2)	
Visit Window	(-6 months to +14 Days)	(±14 days)
Informed Consent a	X	–
CT Scan of Chest	X	X
a informed consent for this sub-study must take place after the subject has been enrolled and randomized into the INS-212 study. This will be a separate informed consent from the INS-212 main study. b Computed tomography of the chest at Baseline (Day 1) is performed only for those subjects whom have signed the CT Scan Sub-Study informed consent if not completed within 6 months before the first dose of LAI or multi-drug regimen at the Baseline (Day 1) visit. EOT scan is required if no less than 6 months have elapsed since the previous CT scan was performed.		

Protocol Amendment #3 version: 22 February 2016

*This protocol is solely for the purpose of communicating information about the investigational drug between Insmmed Incorporated and study personnel. Information is not to be reproduced, abstracted or used for sharing of information for any other purpose, whatsoever, except with the written permission of Insmmed Incorporated.*

Confidential

APPENDIX 5

JAPAN SPECIFIC CT SCAN SUB-STUDY

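### The chest CT analysis needs a Baseline value that the protocol does not specify, its missing-scan rule lets the Baseline scan stand in for EOT, and the Japan EOT scan rules conflict

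*Protocol*

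**What the plan says.** **Analysis.** Section 9.6.3 puts CT change at EOT in the same sentence as change in walk distance and in BMI. All are to be analysed by ANCOVA with the comparison arm "and the randomization strata as factors, and the corresponding Baseline measure as a covariate". For a missing EOT scan the rule is: "If a CT scan is not performed at EOT for any subject, then prior CT scan will be used in the analysis".

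**Data recorded.** Appendix 4, Sub-Study Procedures, states: "All chest CT scans will be read locally and a description of findings for each scan will be entered into the eCRF page". It continues: "An overall assessment of improved, worsening, or no change from previous scan will be reported for all scans", restricted to scans after Baseline. Appendix 5 has the same recording rule for Japan.

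**Global schedule.** Table 14-3 lists two scans, Baseline and EOT. Its footnote says: "EOT scan is required if no less than 6 months have elapsed since the previous CT scan was performed". Appendix 4 applies the condition to early stoppers, "which includes any subject that prematurely discontinues study drug provided that more than 6 months have elapsed since their last CT scan". Section 6.7 limits their scan to those "participating in the CT scan sub-study but only if 6 months or more have elapsed". An older scan may serve as the "Baseline measure if this CT scan was obtained within 6 months from the subjects Day 1 study visit", and a new one may be taken up to 14 days after the first dose.

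**Japan schedule.** Appendix 5, Sub-Study Design, lists scans at Months 6, 12 and EOT without condition. Section 6.7 likewise asks for a Month 16 scan, with a reference to the appendix. Appendix 5, Sub-Study Procedures, and Table 14-4 footnote b make the EOT scan depend on 6 months having passed since the last one. Objective 1 of that sub-study compares Baseline with EOT.

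**The concern.** Three parts of the protocol do not fit together.

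1. An ANCOVA with a Baseline covariate needs a Baseline value on the same scale as the outcome. Walk distance and BMI have one. For CT the protocol specifies only a description of findings at Baseline.
2. A rule that uses the prior scan, with no limit on which scan, can select the Baseline scan as the EOT result. The comparison would then be of Baseline with itself.
3. In Japan the text disagrees on whether the EOT scan is due. A rating made against the previous scan also does not chain into a Baseline-to-EOT comparison.

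At stake are exploratory endpoint 10 and the Japan CT endpoint in Appendix 5. No primary, secondary or key safety inference depends on them.

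**Working it through.** The protocol gives no power or sample-size figure for the CT endpoint (Appendix 4 only expects at least 60 participants), so there is no planned figure to reproduce. The check compares the sections and the scan timing.

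**1. Model against data**

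| Needed by Section 9.6.3 | Specified in Appendices 4 and 5 |
|---|---|
| Change at EOT | Three-level rating against the previous scan |
| Baseline measure | Description of findings; no score or grade |

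The covariate has no specified value, and the only graded outcome is an ordered category.

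**2. When the global rule reaches the Baseline scan**

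Let T be the month of the EOT scan and a the age of the Baseline scan in months at Day 1 (negative if taken later). The gap is T + a, and the EOT scan is waived if T + a < 6.

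- a = 0: waived if T < 6
- a = 3: waived if T < 3
- a = 6: practically never waived
- a = -0.5 (14 days after first dose): waived if T < 6.5

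For EOT at Month 8, taking 30.4 days per month, the smallest gap is 8 × 30.4 - 14 (EOT window) - 14 (late Baseline) = 243.2 - 28 = 215.2 days. Six months is 6 × 30.4 = 182.4 days, so the scan is due. The waiver against Baseline therefore affects only subjects with an early EOT visit. A missed EOT scan can occur at any time. In both cases Baseline is the only scheduled earlier scan in Table 14-3. It carries no rating, so the substitution yields an unrated value, or a zero change only if someone assigns it by construction.

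A non-study scan taken after Baseline and within 6 months before EOT can also be the prior scan. There the rule works as it should.

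**3. Japan timing**

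- Subjects leaving at Month 8 (the EOT visit for non-converters and relapsers, Table 3-1 footnote l): 8 - 6 = 2 months since the Month 6 scan; at most 2 months + 3 + 14 days with the Table 14-4 windows.
- Converters: conversion needs three monthly negatives by Month 6, so the first falls at Month 1 to 4. EOT is 12 months later, at Month 13 to 16. The gap from the Month 12 scan is 1 to 4 months; at most 4 months + 3 + 14 days = 4 months 17 days, or 4 months 19 days with the 5-day Month 12 window of Section 6.5.

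All are below 6 months. On-schedule subjects are due an EOT scan under one reading and not under the other.

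**4. What the last Japan rating measures**

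- EOT scan done: the rating is against Month 12 (converters) or Month 6 (Month 8 leavers).
- EOT scan not done: the last rating is Month 12 against Month 6 (converters), or Month 6 against Baseline (Month 8 leavers).

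None of these is a rating of EOT against Baseline. The last case comes closest but stops at Month 6. Section 9.6.3 does not say whether it also governs the Japan sub-study; steps 3 and 4 do not depend on that.

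**The case against.** **The eCRF or SAP may supply the score.** The eCRF page is not shown, the sponsor keeps the scans, and the SAP may code the descriptions. This stands as a limit: the finding is about what the protocol specifies. But the conflict lies between Section 9.6.3 and the appendices, so it is more than a detail left to the SAP.

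**The prior-scan rule serves the waiver.** It is natural to use a recent scan when the EOT scan is waived because of it. That stands for post-Baseline scans. The text does not stop there, and the remaining case is narrow.

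**Appendix 5 governs Japan.** Section 6.7 refers to the appendix for Japan procedures, and the condition appears there twice. That weakens the reliance on Section 6.7, but the unconditional list is also inside Appendix 5. Nor is the condition empty. A subject stopping at Month 4 with a Baseline scan 3 months old has a gap of 4 + 3 = 7 months. One who missed Month 12 and reaches EOT at Month 13 has 13 - 6 = 7 months. The contradiction concerns on-schedule subjects. Descriptions and retained images would also permit a later comparison with Baseline, but the specified rating does not provide one.

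**Stronger readings.** A reader might infer that the rule fills the data with false unchanged results. Baseline scans have no rating, so that needs a further scoring step which the protocol does not state. A reader might also take the gap between 351 randomized and 261 evaluable subjects as a rate of early EOT visits. Section 3.6.1 defines evaluable by monthly culture results, so it says nothing about CT scans. Finally, a reader might expect a bias against LAI from early stopping. No rate of waived or missed scans by arm is given, and Section 5.12 lets subjects outside Japan who stop drug stay until Month 8.

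**Conclusion.** The point holds as a minor one, for exploratory endpoint 10 and the Japan CT endpoint only. The ANCOVA cannot be run on the category the protocol collects. The substitution rule fails to exclude a Baseline scan that has no rating. The Japan text is inconsistent on the EOT scan for on-schedule subjects, and their last rating does not deliver objective 1.

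The size and direction of any distortion cannot be derived from the documents. The conclusion assumes that no Baseline CT score is defined elsewhere, such as on the eCRF page. If one is, the covariate problem falls away, but the substitution wording and the Japan conflict remain.

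**What to change.** - **Analysis (Section 9.6.3).** Analyse the three-level result with a stratified categorical or ordinal method, for example a CMH mean-score test by the randomization factors, without a Baseline covariate. Other ordinal methods would also serve. With about 60 subjects over four strata, some strata may be sparse.
- **Data.** Add one eCRF item in which the local reader rates each follow-up scan against Baseline. It matters most in Japan, where the previous scan is often not Baseline.
- **Substitution.** Replace the sentence with: *Only a post-Baseline scan obtained within the 6 months before EOT may replace a missing EOT scan, using its rating against Baseline; the Baseline scan is never used as the EOT scan; subjects without such a scan are treated as missing and counted by arm.*
- **Japan.** Reconcile Section 6.7, the Sub-Study Design and Sub-Study Procedures of Appendix 5, and Table 14-4 on the EOT scan.

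The cost is wording and one eCRF item. The first three changes need no extra scans; the Japan reconciliation could change the number of scans, depending on how it is settled. The downside is that fewer subjects contribute, with possible selection after randomization, which should be stated when reporting. The item is best added while scans are still being read, because a rating not collected is harder to recover later.

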## **9.7 SAFETY ANALYSIS**

Safety data will be summarized for the Safety Population.

Adverse events will be coded using the agreed upon version of the Medical Dictionary for Regulatory Activities (MedDRA). For non-converters entering the single arm LAI study (Study INS-312), safety monitoring will continue as defined in that protocol. The number and percent of subjects with treatment emergent AEs by system organ class and preferred term will be presented by treatment arm. The severity of the AEs, the relationship to the investigational

Protocol Amendment #3 version: 22 February 2016

*This protocol is solely for the purpose of communicating information about the investigational drug between Insmmed Incorporated and study personnel. Information is not to be reproduced, abstracted or used for sharing of information for any other purpose, whatsoever, except with the written permission of Insmmed Incorporated.*

product, AEs causing study discontinuation, and all treatment emergent SAEs will be similarly presented. Fatal SAEs will also be presented separately in a similar manner.

Vital signs (temperature, systolic and diastolic blood pressure, pulse, pulse oximetry, and respiratory rate) results will be descriptively summarized by treatment arm.

Clinical laboratory test and pulmonary function results will be descriptively presented. Shifts of laboratory results from Baseline (Day 1) to Month 6 and EOT will be presented by treatment arm.

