## 3 INVESTIGATIONAL PLAN

### 3.1 STUDY DESIGN

The Screening window allows time for sputum culture results, susceptibility by minimum inhibitory concentration (MIC) determination, and scheduling of Screening assessments. Any delay in obtaining microbiological results and MICs must be reported to the Sponsor immediately and documented within the study source documents. In the event that sputum culture results are not known by 8 weeks (Day -14), the Baseline (Day 1) visit should be scheduled as soon as possible in order to maintain the Screening window, and an extension of the Screening window to 14 weeks is allowed, if necessary. If sputum culture results are known prior to 8 weeks (Day -14), the Screening window of 10 weeks must be maintained. Once Screening assessments are complete and sputum culture results are known, eligible

Protocol Amendment #3 version: 22 February 2016

*This protocol is solely for the purpose of communicating information about the investigational drug between Insmid Incorporated and study personnel. Information is not to be reproduced, abstracted or used for sharing of information for any other purpose, whatsoever, except with the written permission of Insmid Incorporated.*

Confidential

subjects will be randomized 2:1 to LAI administered QD plus a multi-drug regimen or a multi-drug regimen alone. The primary endpoint will assess culture conversion by Month 6.

Sputum culture results will only be available to the site after the Month 6 sputum result is known, in time for the Month 8 visit. At Month 8 (-28 to +7 days), after all sputum culture results are known, up to and including Month 6, subjects will be assessed as converters or non-converters.

All converters will remain in Study INS-212 (Section 4.6). All converters who, after culture conversion, subsequently have MAC-positive sputum cultures in liquid broth media (agar negative) for 1 or 2 consecutive months only, will also remain in Study INS-212. These subjects will continue on their randomized treatment regimen until they complete a total of 12 months of treatment (EOT), starting from the first of 3 negative cultures that defines culture conversion. These subjects will return after the EOT visit for 28 day, 3, 6 and 12 months off-treatment follow-up visits. The 12 months off-treatment follow-up visit will be the end of study (EOS) visit. No NTM treatment will be administered during the off-treatment phase.

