At Month 8, all non-converters will be discontinued from INS-212 (Section 4.6). All subjects who experienced a relapse or recurrence (Section 4.6) by Month 6 will also be discontinued from INS-212 at their Month 8 visit. These subjects may be eligible to enter a separate open-label study of LAI (Study INS-312), provided all entry criteria have been met for that study.

[figure not shown]
Expectorated sputum (spontaneous or induced e.g., with nebulized hypertonic saline solution as needed) will be collected at Day 1 and every month through Month 6, and at Months 8, 12, at EOT, at 28 days, 3, 6 and 12 (EOS) months off-treatment.

All subjects will come in monthly for routine visits through Month 6, at Months 8, 10, 12, 14, EOT, and at 28 days, 3, 6 and 12 (EOS) months off-treatment. Home Healthcare visits may be available at Months 1, 2, and 5 for sites with IRB/EC approval to conduct Home Healthcare visits, and qualifying subjects who may have difficulty attending clinic visits. (At Months 10 and 14 subjects randomized to LAI will return to the clinical site for drug dispensation, and AE and concomitant medication assessments). Unscheduled visits will occur as needed should subjects' symptoms worsen between visits.

Protocol Amendment #3 version: 22 February 2016

*This protocol is solely for the purpose of communicating information about the investigational drug between Insmid Incorporated and study personnel. Information is not to be reproduced, abstracted or used for sharing of information for any other purpose, whatsoever, except with the written permission of Insmid Incorporated.*

Figure 3-1 Study Design

\*All converters (at least 3 consecutive monthly negative sputum cultures by Month 6) will remain in study for 12 months, starting from the first negative culture that defines culture conversion.

\*All non-converters and subjects who experienced a relapse or recurrence after culture conversion will discontinue the study at Month 8 and may be eligible to enter a separate Open-Label study (INS-312).

Protocol Amendment #3 version: 22 February 2016

*This protocol is solely for the purpose of communicating information about the investigational drug between Insmed Incorporated and study personnel. Information is not to be reproduced, abstracted or used for sharing of information for any other purpose, whatsoever, except with the written permission of Insmed Incorporated.*

Confidential

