## **9 STATISTICS**

### **9.1 SAMPLE SIZE**

The sample size was determined for the primary comparison between the treatment arms LAI plus a multi-drug regimen and a multi-drug regimen alone with respect to the proportion of subjects achieving culture conversion by Month 6 using nQuery Advisor® 7.0. Assuming a culture conversion rate by Month 6 of no less than 20% for the LAI plus a multi-drug regimen treatment arm, the rate by Month 6 of 5% for the multi-drug regimen alone treatment arm, and a 2:1 randomization ratio, a sample size of 261 subjects (174 for LAI plus a multi-drug regimen and 87 for the multi-drug regimen) will provide at least 90% power for the continuity-corrected Chi-square test at the 2-sided significance level of 0.05.

Protocol Amendment #3 version: 22 February 2016

*This protocol is solely for the purpose of communicating information about the investigational drug between Insmmed Incorporated and study personnel. Information is not to be reproduced, abstracted or used for sharing of information for any other purpose, whatsoever, except with the written permission of Insmmed Incorporated.*

The sample size was also evaluated for the secondary endpoint of change from Baseline to Month 6 in 6MWT distance. Assuming a common standard deviation of 100 and a 2:1 randomization ratio to either LAI plus a multi-drug regimen or a multi-drug regimen alone, a sample size of 192 subjects (128 for LAI plus a multi-drug regimen and 64 for the multi-drug regimen) will provide at least 90% power to detect a between-treatment difference of 50 meters in mean change from Baseline to Month 6 in 6MWT distance using a two arm t-test at the 2-sided significance level of 0.05.

Due to lack of durability data, it is difficult to estimate the power with a total sample size of 261 subjects for the comparison between treatment arms with respect to the proportion of subjects achieving culture conversion with durability after 3 months off-treatment. Assuming the proportion of subjects achieving culture conversion with durability is 16% and 4% for LAI plus a multi-drug regimen and a multi-drug regimen respectively, and a 2:1 randomization ratio, a sample size of 261 subjects (174 for LAI plus a multi-drug regimen and 87 for the multi-drug regimen) will provide at least 83% power for Fisher's exact test at the 2-sided significance level of 0.05.

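### Section 9.7 compares arms on TEAE percentages with no common time window, although conversion, planned at 20% versus 5%, decides who stays after Month 8

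*Protocol*

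**What the plan says.** **Summary measure.** Section 9.7 fixes the main adverse event summary: "The number and percent of subjects with treatment emergent AEs by system organ class and preferred term will be presented by treatment arm". Severity, relatedness, AEs leading to study discontinuation and SAEs are to be shown the same way. Section 9.5.3 defines the Safety Population as everyone with at least one dose. Section 9.7 gives no cut-off for these tables.

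**Who stays.** Section 3.1: "At Month 8, all non-converters will be discontinued from INS-212". Subjects who relapse or recur by Month 6 "will also be discontinued from INS-212 at their Month 8 visit". The remaining converters continue on their randomized regimen "until they complete a total of 12 months of treatment (EOT), starting from the first of 3 negative cultures" that define conversion. Section 3.6.2 caps treatment at 16 months. These converters then have off-treatment visits up to 12 months after EOT.

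**How many are expected to stay.** Section 9.1 plans on a "culture conversion rate by Month 6 of no less than 20% for the LAI plus a multi-drug regimen treatment arm" and "the rate by Month 6 of 5% for the multi-drug regimen alone treatment arm".

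**AE collection.** Section 7.2.6.1 has AEs sought at every contact, and Table 3-1 schedules AE assessment through the EOS visit. Under Section 5.12.1, subjects who discontinue before Month 12 and do not enter INS-312 have an EOT visit. They are then telephoned for safety 28 days after EOT, at Month 12 and 12 months after EOT. For non-converters who enter INS-312, Section 9.7 moves safety monitoring to that protocol.

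**The concern.** A percentage of subjects with at least one event compares two arms fairly only if both are observed for about the same time. Here the efficacy outcome sets the observation time, and the plan expects that outcome four times as often on LAI. If LAI works as planned, the LAI denominator carries more time at risk, and its percentages rise somewhat even when the drug adds no risk.

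At stake is how the tolerability tables of an open-label trial are read, including SAEs and the ototoxicity and nephrotoxicity terms that Section 8.3 lists as of special interest. Part of any LAI excess could be a by-product of efficacy, and the table in Section 9.7 could not show how much. Elsewhere the protocol ties comparisons to time: mortality is analysed by Kaplan-Meier and a stratified log rank test (Section 9.6.3), and laboratory shifts are tied to Month 6 and EOT (Section 9.7). AE incidence has no such anchor.

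**Working it through.** **1. The planning rates reproduce the stated sample size.** With 5% versus 20%, 2:1 allocation, two-sided 0.05 and 90% power, the pooled rate is (0.05 + 2 × 0.20)/3 = 0.15. The uncorrected control-arm size is

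[1.96·√(1.5 × 0.15 × 0.85) + 1.2816·√(0.05 × 0.95 + 0.20 × 0.80/2)]² / 0.15² = 76.8.

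The continuity correction multiplies this by ¼·[1 + √(1 + 6/(76.8 × 2 × 0.15))]², giving 86.5, so 87 control and 261 in total. Section 9.1 has the same total, split 174 to 87, and claims that it "will provide at least 90% power for the continuity-corrected Chi-square test at the 2-sided significance level of 0.05". The rates used below are therefore the plan's own.

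**2. Planned on-treatment time.** The first of three negative cultures by Month 6 falls between Month 1 and Month 4, so converters reach EOT at Month T = 13 to 16. All others leave at Month 8. Mean time is p·T + (1 − p)·8, before early dropout.

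| EOT | LAI (p = 0.20) | Control (p = 0.05) | Ratio |
|---|---|---|---|
| Month 13 | 9.0 | 8.25 | 1.09 |
| Month 14.5 | 9.3 | 8.325 | 1.12 |
| Month 16 | 9.6 | 8.4 | 1.14 |

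**3. Effect on the percentages.** The documents give no AE hazard, so the 8-month risk r is an assumption and is varied. Under the same constant hazard in both arms, the percent with an event is p·[1 − (1 − r)^(T/8)] + (1 − p)·r. The spurious LAI excess is then 0.15·(1 − r)·[1 − (1 − r)^((T−8)/8)].

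| r | EOT Month 13: LAI vs control, % (excess, points) | EOT Month 16: LAI vs control, % (excess, points) |
|---|---|---|
| 1% | 1.12 vs 1.03 (0.09) | 1.20 vs 1.05 (0.15) |
| 5% | 5.60 vs 5.15 (0.45) | 5.95 vs 5.24 (0.71) |
| 10% | 11.15 vs 10.29 (0.86) | 11.80 vs 10.45 (1.35) |
| 20% | 22.08 vs 20.52 (1.56) | 23.20 vs 20.80 (2.40) |
| 30% | 32.80 vs 30.70 (2.10) | 34.20 vs 31.05 (3.15) |

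With EOT at Month 14.5, the excess is 0.12 and 0.58 points for r = 1% and 5%, and 1.1, 2.0 and 2.6 points for r = 10%, 20% and 30%.

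**4. Falling hazards.** If the hazard halves after Month 8, with EOT at Month 16, the excess is 0.7, 1.3 and 1.7 points for r = 10%, 20% and 30%. With 0.05 per month to Month 8 and one tenth of that afterwards (EOT Month 14.5), it is 0.15 × e^(−0.4) × (1 − e^(−0.005 × 6.5)) = 0.3 points. Keeping 0.05 throughout gives 2.8 points.

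**5. If off-treatment AEs count.** Converters are then observed to Month 25 to 28. The result depends on the Section 5.12.1 calls.
- No Month 8 leaver reached or counted: 11.4 vs 8.85 months (+29%) for EOT Month 13, 11.7 vs 8.925 (+31%) for Month 14.5, 12.0 vs 9.0 (+33%) for Month 16.
- Every leaver observed to Month 20 and those AEs counted (EOT Month 14.5): 0.2 × 26.5 + 0.8 × 20 = 21.3 against 0.05 × 26.5 + 0.95 × 20 = 20.325 months, or +5%.
- Half of them (EOT Month 16): 16.8 vs 14.7 months, or +14%.

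**6. Does the remedy work?** Under equal constant hazards, a cut at Month 8 gives r in both arms. Exposure-adjusted rates also agree: for r = 10%, −ln(0.9)/8 = 1.32 per 100 person-months in each arm.

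**The case against.** **This belongs in the SAP.** Section 9.4 leaves details of tables to a SAP, which is not at hand. Section 9.7 never says that percentages run over the whole study, and it excludes no by-period or exposure-adjusted table. This has force: the SAP may already contain the remedy, and the remedy does not contradict Section 9.7. What stands is that the one between-arm AE measure the protocol fixes is poorly matched to a design in which efficacy sets follow-up.

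**Month 8 leavers are still followed.** Section 5.12.1 gives safety calls to those not entering INS-312. This stands for any comparison that includes off-treatment time. It does not touch the on-treatment imbalance.

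**The effect is small and early events dominate.** Section 5.3 says local respiratory events became less frequent with continued use in prior LAI studies, so the common tolerability events should be little affected. For individual preferred terms with low risk the excess is below one point. This also stands.

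**LAI dropout could cancel it.** Subjects who cannot tolerate LAI stop it (Section 5.4), and in Japan they also leave the study (Section 5.12). Equalising mean on-treatment time needs an excess LAI dropout of 0.15·(T − 8)/(8 − m) at Month m. With m = 2 to 4, that is 20 to 30 percentage points for EOT at Month 16 and 12.5 to 19 points for Month 13. The discontinuation allowance in Section 3.6.1 (351 randomized for 261 evaluable, 25.6%) is not split by arm, so a partial offset is possible. One unplanned imbalance offsetting another would still not make the percentages easier to read.

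**It cannot hide harm.** The summary is descriptive, with no between-arm safety test, and the distortion runs against LAI. That limits the seriousness but does not remove the point.

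**Conclusion.** The point holds at modest size. Following Section 9.7 as written, at the plan's own conversion rates, gives LAI about 9% to 14% more planned on-treatment time. Under equal constant hazards, that adds about 0.1 to 0.7 points to LAI percentages for events with an 8-month risk of 1% to 5%, and about 0.9 to 3 points at 10% to 30%. These figures assume no early dropout and that all converters stay. Relapsers by Month 6 also leave, so the true shares staying are somewhat below 20% and 5%, and the effect shrinks in proportion.

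A reader might infer more: that LAI is observed about a third longer, that its percentages will be inflated by many points, or that the safety comparison as a whole is invalid. The documents do not support this. The 29% to 33% figure requires that off-treatment AEs count and that no Month 8 leaver is reached by telephone or counted. With every leaver reached and counted it falls to about 5%. Section 9.7 sets no end to the treatment-emergent window, so neither extreme is fixed. Nor is it certain that observed LAI percentages will be inflated, since falling hazards and higher LAI dropout both work against it.

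The change is worth making because it is cheap and because, in an open-label trial, a window chosen after the data are seen would look selective.

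**What to change.** In Section 9.7:

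1. Make Day 1 to the Month 8 visit the main between-arm comparison for TEAEs, SAEs and AEs of special interest. This is the period planned for both arms regardless of conversion.
2. For the full treatment period, add exposure-adjusted incidence rates by arm (events per subject-year). These should supplement the Month 8 comparison and not replace it: if hazards fall over time, the longer LAI exposure adds low-risk time and lowers the LAI rate.
3. Show events after Month 8 and off-treatment events in separate tables. State whether AEs learned from the Section 5.12.1 telephone contacts are included.

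If the SAP already does this, a one-line reference in Section 9.7 is enough. The cost is a few extra tables from data already collected, with no new visits, subjects or assessments.
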